5.2. Exclusion Criteria

The Novoglan-01 study exclusion criteria are as follows.

1. Any known allergy to latex or silicones
2. Any bleeding, ulcer or active infection of the penis
3. Any prior prepuce surgery, except for frenuloplasty
4. Any hypospadias
5. Any severe scarring of the glans or foreskin
6. Any history of penile cancer
7. Participants with a history of a psychological illness or other conditions which may interfere with their ability to understand the study requirements

6. STUDY PROCEDURES

6.1. Study Flow Chart

Pre-study enrolment visit – Eligibility and enrollment

Study visit 1 – Minimum 7 days post enrolment visit - Quality of life questionnaire, phimosis measurement, Novoglan product supply and training

Study visits 2 and 3 by phone - Follow-up phone call to review treatment progress and any adverse event or complication at Week 1 and Week 4 post Study visit 2

Final study visit – Quality of life questionnaire, phimosis measurement, any report of complication or adverse event and treatment tolerability questionnaire – End of participant study

6.2. Investigation Plan

Methodology

This section clearly describes how the study procedures/interventions will be conducted in order to ensure the results are reproducible. It includes a table listing all the potential study visits and the procedures that will be conducted at each visit.

Interventions	Enrolment Visit	Visit 1	Visit 2 (phone)	Visit 3 (phone)	Final Study Visit
Timing	Week 0	Week 1	Week 2	Week 5	Week 7 to 9
Baseline demographics	✓				
Medical history	✓				
Concomitant medications	✓		✓	✓	✓
Inclusion / Exclusion criteria	✓				
Participant Consent	✓				
Phimosis measurement		✓			✓
Quality of life questionnaire		✓			✓
Novoglan supply and training		✓			
Treatment progress, adverse event or complication			✓	✓	✓
Treatment tolerability questionnaire					✓

The participant journey during the Novoglan-01 study can be described as follows.

Enrolment visit

Potential participants identified during the Novoglan-01 recruitment process will be seen by the Principal Investigator, [name], during the Enrolment Visit. At that time, the following information will be collected from the participant:

- Demographics including date of birth, race and ethnicity
- Medical and medication history, with particularly focus on phimosis
- Penile examination to confirm phimosis and medical examination including height and weight measurements
- Review of eligibility for the Novoglan-01 study against inclusion and exclusion criteria

If the participant meets the eligibility criteria, [name] will propose participation into the Novoglan-01 study, explain the study, explain the informed consent and review with the participant the informed consent form, pointing out the option of withdrawal at any time and the minimum delay of 1 week between Enrolment Visit and Study Visit 1 to provide sufficient time for careful consent consideration.

At that time, participants wanting to participate in the Novoglan-01 study will:

- Sign the Novoglan-01 Informed Consent Form (see details in Section 9)
- Be asked to make an appointment for Study Visit 1 with the Clinical Trial Nurse
- Be assigned a Novoglan-01 Study unique participant identifier

If the participant agrees to participate to the Novoglan-01 Study, all the above information will be recorded by [name] in the Participant Case Report Form (see details further in Section 9).

Study Visit 1

At Study Visit 1 the participant will meet with the Clinical Trial Nurse who will:

- Carry out a measurement of the participant phimosis using the standard measurement scale based on Kikiros *et al.*, 1993 and using the Novoglan-01 Study Phimosis Measurement Form (see details further in Section 9)
- Carry out an evaluation of the participant quality of life prior to treatment and using the Novoglan-01 Quality of Life Questionnaire (see details further in Section 9)
- Supply the participant with Novoglan investigative product in sufficient quantity for the duration of the study, explain the various components of the Novoglan product and train the participant in its appropriate and safe use (see details further in Section 9)
- Hand out to the participant a printed “how to use” guide for the Novoglan product (see details further in Section 9)
- Schedule a date and time for the Study Visit 2 by telephone

Study Visit 2 – By phone

At Study Visit 2, the Clinical Trial Nurse will phone the participant to inquire and record in the participant Case Report Form about the following points:

- Overall progress with treatment by the participant and any problem in using the Novoglan product requiring further clarifications or training
- Any report by the participant of any adverse effect
- Any change to the concomitant medication list provided at the Enrolment Visit

The Clinical Trial Nurse will conclude the Study Visit 2 phone call by confirming a date and time for the Study Visit 3 phone call.

NOTE: During the phoned Study Visit 2 the participant will be offered the option to schedule a face-to-face follow-up training with the Clinical Trial Nurse at Macquarie University Hospital. If carried out, the outcome of such a follow-up training will be recorded in the Study Visit 2 Case Report Form.

Study Visit 3 – By phone

At Study Visit 3, the Clinical Trial Nurse will phone the participant to inquire and record in the participant Case Report Form about the following points:

- Overall progress with treatment by the participant and any problem in using the Novoglan product requiring further clarifications or training
- Any report by the participant of any adverse effect
- Any change to the concomitant medication list provided at the Enrolment Visit

The Clinical Trial Nurse will conclude the Study Visit 3 phone call by confirming a date and time for the Final Study Visit.

NOTE: During the phoned Study Visit 3 the participant will be offered the option to schedule a face-to-face follow-up training with the Clinical Trial Nurse at Macquarie University Hospital. If carried out, the outcome of such a follow-up training will be recorded in the Study Visit 3 Case Report Form.

Final Study Visit

At the Final Study Visit, the participant will initially meet with the Clinical Trial Nurse and subsequently with the Principal Investigator, [name].

The Clinical Trial Nurse will investigate and record in the participant Case Report Form the following information:

- Measurement of the participant phimosis at study end using the Novoglan-01 Study Phimosis Measurement Form (see details further in Section 9)
- Evaluation of the participant quality of life at the end of treatment and using the Novoglan-01 Quality of Life Questionnaire (see details further in Section 9)
- Evaluation of the participant perceived tolerability of the Novoglan product during the treatment and using the Novoglan-01 Novoglan Treatment Tolerability Questionnaire (see details further in Section 9)

After meeting with the Clinical Trial Nurse, the participant will meet with the Principal Investigator, [name], to review the outcomes of his Novoglan treatment and sign the Novoglan-01 Participant Completion section on the Final Study Visit case report form (see details in Section 9).

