11.1.	Investigator Authorisation Procedure.....	21
11.2.	Participant Protection	21
12.	SAFETY	21
12.1.	Adverse Event Reporting.....	21
12.2.	Serious Adverse Event Reporting	22
12.3.	Data Safety and Monitoring Committee (DSMC)	23
12.4.	Early Termination	23
13.	BLINDING AND UNBLINDING.....	23
14.	CONFIDENTIALITY AND STORAGE AND ARCHIVING OF STUDY	23
15.	TRIAL SPONSORSHIP AND FINANCING.....	23
16.	INDEMNITY	24
17.	KEY REFERENCES.....	24
18.	APPENDICES.....	24

Summary

Study title:

Novoglan-01 clinical trial to confirm the safety, efficacy and tolerability of the Novoglan product in treating adult phimosis

Protocol version: 2.1

Objectives

Primary objective: Confirm the efficacy of the Novoglan product as measured by the improvement in foreskin retraction against a standardised scale.

Secondary objectives: Confirm the safety and satisfaction with treatment as assessed by quality of life improvement and treatment tolerability.

Study design

Single arm, observational prospective trial

Planned sample size

Single cohort of 24 participants

Selection criteria

Participants 18 years or older consulting the Macquarie University Hospital and Princess Alexandra Hospital Urology Clinics with symptoms of adult phimosis, inability to fully retract the foreskin accompanied with pain or discomfort and including participants with prior frenuloplasty or Balanitis Xerotica Obliterans.

Study procedure

Enrolment Visit – Participant meets with physician who confirms eligibility criteria, measures the degree of phimosis and enrolls the participant into the study.

Study Visit 1 – Participant meets with clinical trial nurse for phimosis measurement, to complete the Quality of Life questionnaire and receive training and Novoglan materials and documentation.

Study Visit 2 and 3 – By phone between the clinical trial nurse and the participant at Week 1 and Week 4 post Study Visit 1 to review treatment progress.

Final Study Visit – At 6 to 8 weeks following Study Visit 2, participant meets with clinical trial nurse to measure foreskin retraction, complete the treatment tolerability questionnaire and the quality of life questionnaire – End of participant study

Statistical considerations Sample size calculation - As described in Section 8.
Analysis plan – As described in Section 8.

Duration of the Study

Completion by February 2022 from study start in September 2019

PREAMBLE – Clinical trial contributors and contact details

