recommend the use of steroid creams or circumcision. The professional guidelines from the BAUS refer physicians to the guidelines published by the European Association of Urology (EAU) [EAU Guidelines, 2016] which address phimosis in the section dedicated to paediatric urology. The treatment recommendations include the use of steroid creams and if unsuccessful, the circumcision of the penis.

The main problem with using steroid creams to treat phimosis is the narrow range of stretching motion that will provide suitable stimulation for the foreskin to grow without exacerbating the inflammation or tearing of the foreskin. Recently, a new conservative treatment option, the Novoglan product, has shown promising results, with a very high success rate and satisfaction reported by users. The Novoglan product is designed to be used by participants 18 years and over. Its main component is a small balloon that can be inserted underneath the opening of the foreskin and progressively inflated while avoiding the complications frequently observed with the use of steroid creams. The Novoglan balloon is guided under the foreskin between the glans and the inner side of the foreskin (prepuce) using a purpose moulded rod. Once the balloon is in place the rod is removed and the stop cock and plunger is attached to the Novoglan device. The balloon is inflated by pressing the plunger. The procedure is painless and pressure is under the control of the user to ensure no discomfort. Foreskin cells are placed under tension and tight junctions are loosen under stretching leading to tissue adaptation and cell mitosis. This process increases the column of foreskin cells and increases the foreskin circumference. Treatment is continued for a period of 4 to 8 weeks until full normal retraction is achieved.

The Novoglan product is a medical device commercialised in Australia since 2006 and listed with the Australian Therapeutics Goods Administration (ARTG 168962). The Novoglan product has been used successfully in the Urology Clinic in the past year at Macquarie University Hospital but only with a few adult male participants. The observation of these few adult participant treatments indicated that the Novoglan product is simple and safe to use, effective at treating adult phimosis and comparatively inexpensive. It appears that the Novoglan product produces relief from the symptoms of phimosis in 3 to 4 weeks.

References, in order of citation, are as follows.

The prepuce.

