7. OUTCOMES

7.1. Definition of Outcomes

The expected outcomes from the Novoglan-01 study are as follows.

- Confirmation of the ability of the Novoglan product to effectively relieve phimosis as measured by foreskin retraction before and after treatment against the Phimosis Measurement Scale used at Study Visit 1 and Final Study Visit.
- Confirmation of the safety of the Novoglan treatment as evidenced by the lack of any severe adverse effect or any complication during treatment.
- Confirmation of the satisfaction of participants with the Novoglan treatment as measured by improved quality of life measured by questionnaire filled in by the participants before and after treatment.
- Confirmation of the tolerability of the Novoglan treatment as measured by the treatment tolerability questionnaire filled in by the participants during the Final Study Visit.
- Confirmation of the Novoglan treatment as a valid conservative first line treatment alternative to steroid creams in adult males presenting with phimosis.

Additionally, the publication of the Novoglan-01 study results at urology conferences and in a peer review journal is likely to encourage a review of clinical recommendations in the treatment of adult phimosis. Phimosis treatment guidelines published by the British Association of Urological Surgeons (BAUS) discourage the manual stretching of the foreskin and recommend the use of steroid creams or circumcision. The professional guidelines from the BAUS also refer physicians to the guidelines published by the European Association of Urology (EAU) which address phimosis in the section dedicated to paediatric urology.

Assuming a positive outcome from the Novoglan-01 study that demonstrates the safety, efficacy and tolerability of the Novoglan product in adult phimosis, the aim would be to:

- Convince the phimosis treatment guidelines published by the Urology Society of Australian and New Zealand (USANZ), EAU or BAUS to include a section dedicated to the treatment of adult phimosis.
- Convince the phimosis treatment guidelines published by the USANZ, EAU or BAUS to list the Novoglan product as a recommended conservative treatment for adult phimosis

Finally, the publication of the Novoglan-01 study results is likely to position MQ Health as the centre of reference for adult phimosis treatment in Australia. It is also likely to stimulate similar studies in Australia and overseas.

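### The only post-treatment phimosis grade can fall before a man's course is over, and its date is confirmed only after his progress has been heard

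*Protocol*

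**What the plan says.** The primary outcome compares two grades: "foreskin retraction before and after treatment against the Phimosis Measurement Scale used at Study Visit 1 and Final Study Visit". The section 6.2 table shows no other phimosis measurement.

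The device is handed over at Visit 1: "Study visit 1 – Minimum 7 days post enrolment visit - Quality of life questionnaire, phimosis measurement, Novoglan product supply and training". That table puts Visit 1 at Week 1, the phone visits at Weeks 2 and 5, and the Final Study Visit at Week 7 to 9. The Summary counts the last visit from a different point: "At 6 to 8 weeks following Study Visit 2, participant meets with clinical trial nurse to measure foreskin retraction".

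The one statement of course length is in the background section: "Treatment is continued for a period of 4 to 8 weeks until full normal retraction is achieved". The same section adds: "It appears that the Novoglan product produces relief from the symptoms of phimosis in 3 to 4 weeks".

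On appointments, section 6.2 has Visit 1 arrange Visit 2 and the Visit 2 call arrange Visit 3. The Visit 3 call opens with questions about progress and closes thus: "The Clinical Trial Nurse will conclude the Study Visit 3 phone call by confirming a date and time for the Final Study Visit". The Clinical Trial Nurse makes these calls and takes the final measurement. Section 13 confirms that the study is open label.

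**The concern.** A before-and-after comparison needs a clear meaning for the after state. Here that state rests on one grade per man, at a visit tied neither to the end of his own course nor to a fixed day after supply. Depending on the date, the grade may describe a man still treating, one who has just finished, or one who has been off the device for some weeks.

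The booking step adds a second problem. On the table, the Visit 3 call comes four weeks after supply, about when relief is expected and when the shortest stated course ends. The date is confirmed once progress has been discussed. If slow responders were given late dates, the result would tilt towards the device; early dates for them would understate it. There is no control arm to share such a shift. An analysis can adjust for visit day, but it cannot recover time since last use if that was never recorded.

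**Working it through.** **Inputs.** Supply at Visit 1, Week 1; Visit 2 at Week 2; Visit 3 at Week 5; Final Study Visit at Week 7 to 9 (section 6.2 table). Final Study Visit 6 to 8 weeks after Visit 2 (Summary). Course of 4 to 8 weeks (background).

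**1. The plan's own window.** The table's Week 7 to 9 is reproduced only if the 6 to 8 weeks run from Visit 1: 1 + 6 = 7 and 1 + 8 = 9. Run from Visit 2, as the Summary says, they give 2 + 6 = 8 and 2 + 8 = 10, that is Week 8 to 10. The phone visits conflict too. The Summary has them "at Week 1 and Week 4 post Study Visit 1 to review treatment progress". The section 6.1 flow chart has them "at Week 1 and Week 4 post Study visit 2", which dates Visit 2 from itself.

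**2. Weeks from supply to final grade.**
- Table: 7 − 1 = 6 to 9 − 1 = 8 weeks.
- Summary: 1 + 6 = 7 to 1 + 8 = 9 weeks.

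Both windows are two weeks wide and open before week 8.

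**3. A man on the longest stated course, graded at the early edge.**
- Table: 6/8 = 75% done, 8 − 6 = 2 weeks left.
- Summary: 7/8 = 87.5%, about 88% done, 8 − 7 = 1 week left.

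**4. A man who finishes at week 4.**
- Table: 6 − 4 = 2 to 8 − 4 = 4 weeks off the device.
- Summary: 7 − 4 = 3 to 9 − 4 = 5 weeks off.

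**5. If Visit 1 slips.** Section 6.1 sets a minimum gap of 7 days after enrolment and no maximum. If Week 7 to 9 is counted from enrolment and Visit 1 falls at Week 2, the window is 5 to 7 weeks after supply and closes before week 8.

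**6. Share graded mid-course (illustration only).** Assume course length is uniform on 4 to 8 weeks and the visit day is uniform in the window. The share unfinished is the mean of (8 − V)/4 over visit time V, counted as zero once V passes 8.
- Table: mean V = 7, so 1/4 = 25%.
- Summary: only V from 7 to 8 counts, which is half the window; there the mean is 0.5/4 = 12.5%, so 0.5 × 12.5% = 6.25%, about 6%.
- Visit 1 at Week 2: mean V = 6, so 2/4 = 50%.

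The protocol does not give the real distributions, so these figures show only how sensitive the share is to the schedule.

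**The case against.** Several points on the other side stand.

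- To confirm a date may mean restating one already booked, and the nurse must in any case stay inside the window. The text does not say that progress decides the date. Section 9.4 also refers to more than one research nurse, so the caller and the grader share a role but need not be the same person.
- The 4 to 8 weeks is product background, not a treatment rule of this trial. Use instructions sit in the IP Manual, which is an appendix not shown here. Relief expected in 3 to 4 weeks is not the same as full retraction, but nothing shows that many men would be unfinished at 6 weeks.
- Section 3.1 places the second grade at the end of the man's study participation, which a visit in a defined window satisfies. Section 7.1 speaks of after treatment, and section 6.2 labels the quality-of-life score from the same visit as end of treatment. The wording is loose, but no passage claims to estimate the effect of a full course.

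A reader might infer three stronger things that the documents do not support. The first is that scheduling alone spreads men over 0 to 4 weeks off the device. That spread comes mainly from course length: with everyone graded at 8 weeks it is still 8 − 8 = 0 to 8 − 4 = 4 weeks, and the window adds at most 2 weeks for any one man. The second is that the timing is known to inflate efficacy. The direction is open. The third is that no stop date is collected. Treatment progress is a listed item at Visits 2, 3 and Final, and the case report forms are not shown.

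None of this supplies a fixed assessment day, or a rule that separates the date from the progress report.

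**Conclusion.** The point holds as a permitted weakness in timing. On either schedule, the sole post-treatment grade may be taken before the longest stated course is over, at 75% of it on the table or about 88% on the Summary. Its date may be settled in the light of reported progress, by the role that then grades the outcome unblinded. This rests on the background course length, which is the only one in the protocol, and on Visit 1 taking place at Week 1.

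The size of any bias cannot be stated, because actual course lengths and visit dates are unknown. The point does not invalidate the design. It merits a change because the change is cheap and must be made before data are collected.

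**What to change.** 1. Reconcile the Final Study Visit and phone-visit anchors in the Summary, section 6.1 and the section 6.2 table, and reconcile these with the background course length. Treatment length and stopping are for the sponsor to settle.
2. Then set one target assessment day counted from Visit 1, late in the reconciled window and not before the longest stated course ends, with a tolerance of a few days. As the text stands, 8 weeks after Visit 1 lies in both windows: the upper edge of the table's and the middle of the Summary's.
3. Book that day at Visit 1, before any progress is known, and reword the end of the Visit 3 call as a reminder of it.
4. If the case report form does not already do so, record the date of last device use, and describe the primary change by time since last use. This is still needed under a fixed date, because a man who stops at 4 weeks would be 4 weeks off the device when graded at 8.

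The cost is protocol wording and possibly one date field. Some men would attend up to two weeks later than they otherwise would. No visit is added.

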6.3. Study Procedure Risks

The following risk assessment for the Novoglan-01 study was prepared using Trial Risk Assessment for the NSLHD Investigator-led/Collaborative Group Clinical Trials published by the NSW Department of Health, Version 2.0 dated April 2016 (on file at Platigo Solutions).

Additionally, all measures designed to reduce risks are presented in the **Novoglan-01 clinical trial Safety Plan** submitted for review together with the Study Protocol.

- Participant Journey

The participant journey is described above in section 6.2.

- Additional risks with participants' physical integrity and safety

The Novoglan-01 study involves a medical device that is currently listed on the Australian Therapeutics Goods registry under the reference #168962 as a Class 1 (non-sterile) device indicated for the treatment of phimosis in adults. Furthermore, the Novoglan product will be used as per indications in the device TGA listing during the Novoglan-01 clinical trial.

Despite the Novoglan product having been commercialised without any reported adverse event, the Novoglan product safety has never been scientifically analysed and it is therefore reasonable to consider the study risk as Type B or somewhat higher than that of standard of medical care for adult phimosis, the standard of care being either the use of steroid creams or circumcision.

- Safety monitoring of the trial and DSMC

The establishment of a Data Safety and Monitoring Committee (DSMC) is not considered being necessary in view of the Type B risk category of the Novoglan-01 clinical trial and the fact that the Novoglan product will be used as on male adults as per usage instructions described in the listing of the device with the TGA.

- Risks to participants' rights

Risks to participants rights in taking part to the Novoglan-01 study have been assessed and mitigation strategies developed to minimise these risks. The risks evaluated fall into 2 categories and are presented in the following table.

Risks to participants' rights – The consent process		
Risk	Concerns	Risk minimisation strategy
Consent procedure	Does the consent process allow sufficient time for participants to consider their decision and discuss it with third parties	
 • Specific training on the consent/assent process will be provided to the clinical team. • First study visit following participant enrolment will be scheduled at least 1 week following the enrollment visit.

Risks to participants' rights – Protection of personal data		
Risk	Concerns	Risk minimisation strategy
Breach of confidentiality	Identifiable data disclosed inappropriately	
 • Trial conducted by health professionals experienced in clinical trials and their confidentiality requirements • The safety of the confidentiality of participant data including forms used on paper or electronic will be assessed in the Safety and Confidentiality audit conducted

		prior to trial commencement and described in Section 10.2.
--	--	--

- Risks to data integrity

Risks to participants' rights – Risk to data integrity		
Risk	Concerns	Risk minimisation strategy
Data integrity	Protocol violations	
 • Protocol specific training provided at trial start-up meeting • Periodic monitoring visit to include checks of clinical records of eligibility and endpoint data
	Lack of reliability of results and data quality	
 • Measurements of phimosis, quality of life and treatment tolerability using robust methods and designs • Well-designed and unambiguous case report forms • Data management and transfer methods that ensure an audit trail is maintained from the primary data to the database, and from the database to the analysis files (with changes that are controlled, attributable, and properly authorised)

